Study Description: We will randomize 1500 adults aged 60+ to 10 weeks of one of three Step 1 strategies: aripiprazole augmentation, bupropion augmentation, or switch to bupropion. Those who do not attain remission in Step 1 will be randomized to 10 weeks of one of two Step 2 strategies: lithium augmentation or switch to nortriptyline. Those who complete acute treatment will be followed in a one-year continuation. This pragmatic RCT will be carried out in real-world clinical settings. Primary care and mental health clinical partners will provide treatments, with decision support from the study team.

Study population: Participants will be non-demented older adults aged 60+, with equal proportions aged 60-70 and 70+, with current major depression that has failed to respond to 2+ adequate antidepressant trials. We will recruit across five regions: St. Louis and rural Missouri; Los Angeles City and County; Western Pennsylvania; New York City; and Toronto and rural Ontario. Two-thirds of the sample will be women and 70% white, 15% black, 10% Latino, and 5% other racial groups.

Patients will be identified from clinical networks at each of the five participating centers. Our two primary mechanisms of recruitment will be through screening and referrals. We will screen through clinical networks using Electronic Medical Records (EMR) and will contact all patients in practices aged 60 and older who in the recent past were prescribed or are currently taking antidepressants. Referrals will be elicited from practitioners and through in-practice

OPTIMUM Protocol Version 3.0 2019-03-04 Final Version

advertisements to patients and their caregivers specifically asking if the doctor, patient, or caregiver describes the clinical situation as treatment resistant or difficult to treat.

Primary/secondary outcomes: Psychological well-being is the patient-centered effectiveness outcome and remission from depression is the clinician-focused effectiveness outcome. Secondary patient-reported outcomes include physical function and social participation. Safety will be monitored through serious adverse events as well as falls and fall-related injuries. As well, the study will test how aging influences the relative benefits and risks of antidepressants for TRD. Additionally, a qualitative study of patient and clinician partners will provide the lived experience of TRD and antidepressant strategies.

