most experts believe that one of the most efficient ways to decrease suicidal risk in older depressed individuals is to treat their depression. Furthermore, all participants will be formally assessed frequently throughout the study. All sites have a 24/7/365 on-call system with geriatric psychiatry back-up. If the study personnel identify that a participant has become acutely suicidal, this participant will be referred to a mental health professional for further evaluation and treatment. This may lead to a clinical intervention that is lifesaving and may not have occurred had the participant not been participating in the study. We have included a Suicide Risk Management protocol to assess and reduce suicide risk in the manual of procedures as well as a Quick Suicide Safety Screening that may be used during phone pre-screening.

Body Composition Measurement (Washington University site only):

For participants with a pacemaker or a prosthesis that uses any other type of battery-powered or electrical power implant, there is a chance that the measurement of body composition could cause interference with the device. In order to protect from that risk, participants should not take part in the body composition measurement if they have a battery-powered or electrical implant. Participants with a history of abnormal heart rhythms will be reviewed by a medical doctor to make sure that the body composition measurement will not worsen their condition.

1.i Potential Benefits

Participants may or may not benefit from being in this study. Changing medication strategies may provide relief from symptoms of depression. Results from this study will provide doctors and patients with knowledge about the risks and benefits of antidepressant medications for older adults, so that they can make informed choices to manage depression.

1.j Early Withdrawal of Subjects

Participants will be asked to continue in the study for follow-up regardless of their and their physician's adherence to the medication recommendations from the study team. Participants who discontinue study medications for tolerability reasons will be asked to complete the appropriate Acute Phase End Assessments for their phase of the study (see Section F5). Participants who end Step 1 treatment early due to tolerability issues will be invited to proceed to Step 2 after completing Acute Phase End Assessments.

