- Phone Call with Local Research Team (approximately 10 minutes)
 - o PHQ-9
 - Spontaneous side effect report & severity
 - Falls Assessment
 - Adherence
 - o Counselling about adherence and management of side effects.
 - AE reports done as needed.
 - Decision support staff contact study MDs when needed (e.g. if confusion about whether to increase antidepressant dose).
 - Decision support staff contact participant's clinical provider with recommendations;
 also will typically tell patient the recommendations.

F5 Acute Phase End Assessments

- Step 1 Week 10, Step 2 Week 10, or upon early withdrawal (if possible)
 - If there is a long delay between the Step 1 Week 10 assessment and the initiation of Step 2, the participant may be asked to repeat some or all of the Step 1 End assessments.
- *In addition to Decision Support assessments, local research team will conduct the following assessments (in person if possible; approximately 1 ½ hour):
 - NIH Toolbox Psychological Well Being (may be conducted via phone or Redcap survey)
 - PROMIS Physical Function (may be conducted via phone or Redcap survey)
 - o PROMIS Social Participation (may be conducted via phone or Redcap survey)
 - NIH Cognition and Motor Batteries (may be foregone for participants living in remote locations)
 - Weight (self-reported)
- Central Rater Assessments (by phone; approximately 30 minutes. WU participants may do in person or by phone)
 - o MADRS

F6 Continuation Assessments

- Months 4, 8, and 12 after completing acute treatment in Step 1 and/or 2 as indicated.
- Participants who relapse in Continuation after Step 1 may be invited to participate in Step 2; and then continuation subsequently.
- Local Research Team Assessments (in person if possible; approximately 1½ hour)::
 - NIH Toolbox Psychological Well Being (may be conducted via phone or Redcap survey)
 - PROMIS Physical Function (may be conducted via phone or Redcap survey)
 - o PROMIS Social Participation
 - Weight
 - NIH Cognition and Motor Batteries (Month 12 only; may be foregone for participants living in remote locations)
- Central Rater Assessments (by phone; approximately 30 minutes)
 - o MADRS
 - Falls & Related Injuries
 - Spontaneous side effects and severity(discuss with local sites if needed)
 - Adherence

F7 Genetic Testing

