2.2.3. Scope

This Statistical Analysis Plan will be the guiding document for the quantitative analyses that will be conducted in the OPTIMUM study.

3. Study Methods

3.1. General Study Design and Plan:

Participants will be recruited from five regions with diverse and representative populations encompassing approximately 708 adults. The five regions are: St. Louis and rural Missouri; Los Angeles City and County; Pittsburgh and Western Pennsylvania; New York City; and Toronto and rural Ontario. Participants will be non-demented adults aged 60+, with equal proportions aged 60-70 and 70+, with current major depression that has failed to respond to 2+ adequate antidepressant trials. Two-thirds of the sample will be women and 86% White, 7% Black, 8% Latino/Hispanic, and 4% other racial groups.

All recruited adults will be randomized to 10 weeks of one of three Step 1 strategies: aripiprazole augmentation, bupropion augmentation, or switch to bupropion. Those who do not attain remission in Step 1 or those who do not qualify for Step 1 will be randomized to 10 weeks of one of two Step 2 strategies: lithium augmentation or switch to nortriptyline. Those who complete acute treatment will be followed in a one-year continuation, with assessments every four months. This pragmatic RCT will be carried out in real-world clinical settings. Primary care and mental health clinical partners will provide treatments, with decision support from the study team.

Patients will be identified from clinical networks at each of the five participating centers. Our two primary mechanisms of recruitment will be through screening and referrals. We will screen through clinical networks using Electronic Medical Records (EMR) and will contact all patients in practices aged 60 and older who in the recent past were prescribed or are currently taking antidepressants. Referrals will be elicited from practitioners and through advertisements to patients and their caregivers.

An additional mechanism of recruitment will be through IRB-approved hospital network registries and social media advertisements and posts on Facebook and Instagram. Potential participants who see Facebook ads and want to participate in the study can click on the Facebook ad and it will direct them to a secure and encrypted survey website using Redcap to collect name, phone number, and email address. Research study staff will contact the potential participants to screen them for study eligibility.

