3.2. Randomization

Randomization of participants will be implemented in REDCap, using a randomized block design by alternating blocks of 3 and 6 within strata by site (i.e., St Louis vs. Pittsburgh), referral source (primary care vs. specialty mental health) and age (<70 vs >70).

Only assessors of outcome measures will be blinded. Assessors will be instructed to not ask, and participants instructed to not share the treatment to which they were assigned. Participants, providers, and other research staff will not be blinded to treatment conditions.

In this pragmatic design where all levels of adherence are allowed, participants will be considered randomized assuming they meet the eligibility requirements at screening (including any safety screens as applicable) and they have been given a randomization assignment (i.e., even if participants never took a dose of the randomized medication, they will be included in the analysis).

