3.3. Sample Size

Our original proposal was to randomize 1,500 patients in Step 1 and 800 for Step 2. This was adjusted mid-study when it became clear that recruitment efforts would not achieve this sample size. Newly adjusted sample size is 708 (estimated mid-study), including 123 participants who were enrolled into step 2 without first participating in step 1.

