6.2. Analysis methods

To test hypothesis H1a (psychological well-being), a repeated measure of 2*2*3 ANOVA with age (60 – 70, > 70), time (baseline, end of Active phase of Step 1) by treatment group (3 levels) will be used. Specific time * treatment group contrasts will compare the changes across pairs of treatment groups. These tests will be conducted with a Hochberg Step-down procedure. If the comparison with the lowest p-value < 0.05/3 it is significant. If the second lowest p-value is also < 0.05/2 then it also will be significant and if the third p-value is < 0.05 then it also will be significant. We will include site as strata in all analyses. For those who proceed to Step 2, analogous repeated measures 2*2*2 ANOVA will be used with a significance level of .05 for the time*treatment group comparison.

To test hypothesis H1b (remission), a corresponding 2*3 (age by treatment group) generalized linear models with a logit link function will be computed for the dichotomous outcome of remission. Pairwise treatment groups will be compared as in H1a.

To test hypothesis H2a (serious adverse events), Cox models will be used to examine time to event (with Anderson & Grill extensions for repeated events) will compare the treatment arms during both the acute phase and the continuation in terms of serious adverse events. Pairwise comparison between treatment groups will be tested.

To test hypothesis H2b (falls and fall-related injuries), a repeated measures generalized linear model with a cumulative logistic link function. The factors will be treatment group and time (week 2, 4, 6, 8 or 10). The age group (<70 vs.>70) and clinic stratification variables will be included in the model as well as the fall history obtained at baseline. Pairwise comparisons between the treatment group pairs will be formally tested. The same model with a simple logistic link function will be conducted during each 2-week period where the response is a fall-related injury or not.

In terms of the exploratory hypothesis 3, we will include the treatment by age group (<70 vs >70) by time interaction to the linear models described above to test for both the benefits and risks for the treatment alternatives. Additionally, we will fit a model with age as a continuous variable.

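### The SAP states the Step 2 population inconsistently, defines no Step 2 analysis set for 123 direct entrants, and plans no analysis in Step 1 non-remitters alone

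*SAP*

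**What the plan says.** The documents describe who enters Step 2 in several ways.

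- **Protocol A1 (abstract):** "Those who do not attain remission in Step 1 will be randomized to 10 weeks of one of two Step 2 strategies". Protocol E1.b and SAP 5.3 likewise name only people who have not remitted in Step 1.
- **SAP 3.1:** adds a second group, "or those who do not qualify for Step 1 will be randomized to 10 weeks of one of two Step 2" strategies. The same paragraph says that all recruited adults are randomised to Step 1.
- **SAP 3.3:** gives a revised total of 708, "including 123 participants who were enrolled into step 2 without first participating in step 1". SAP footnote 4 confirms the two ways in, and footnote 3 says that seizure disorder and Parkinson's disease were exclusions for Step 1 only while direct entry was open. Protocol V3.0 closed that route.
- **Protocol D2 1.j (and SAP 5.4.1):** "Participants who end Step 1 treatment early due to tolerability issues will be invited to proceed to Step 2".
- **Protocol F6:** "Participants who relapse in Continuation after Step 1 may be invited to participate in Step 2". The SAP does not mention this route.

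The Step 2 analysis is one sentence in SAP 6.2: "For those who proceed to Step 2, analogous repeated measures 2*2*2 ANOVA will be used with a significance level of .05", for the time-by-treatment comparison. The factors are age, time and treatment, and the only other adjustment stated for this model is "We will include site as strata in all analyses". Entry route is not a model term, a subgroup or a sensitivity analysis. The added sensitivity analysis in SAP footnote 1 (no prior trial of a randomised drug) covers Step 1 only.

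**The concern.** Two analysts following this SAP could analyse different Step 2 populations. One would take everyone randomised in Step 2, as SAP 3.1 and the intention-to-treat rule in SAP 4.3 imply. The other would take the phrase about proceeding to Step 2 literally, together with SAP 5.3, and leave out the 123 who never had Step 1.

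The Step 2 baseline is also left open. An analysis described only as analogous to Step 1 does not say whether baseline is the end of Step 1, enrolment (for direct entrants), or a repeated assessment after a delay, which Protocol F5 makes optional.

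If everyone is included, the result averages over groups that differ in known ways. Direct entrants came in under different exclusions. In the protocol's table for the transition from Step 1 to Step 2, the antidepressant to which lithium is added depends on the Step 1 arm, and direct entrants have no row. A clinician deciding what to do after Step 1 fails would want to know whether the result holds in Step 1 non-remitters, and no planned analysis shows that.

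**Working it through.** **Reproducing the plan's Step 2 figures.** Protocol H2 assumes 400 per arm, alpha .05 (taken as two-sided), SD 8 at both times and r = .5. SD of change = √(8² + 8² − 2 × .5 × 8 × 8) = 8. Detectable difference = (z for .975 + z for power) × 8 × √(2/400) = 1.58 at 80% power and 1.83 at 90%; the protocol states 1.6 and 1.8. For remission around 40%, the two-proportion calculation gives 9.8% and 11.4%, as stated. The figures reproduce, but they assume 800 people in Step 2.

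**Share of direct entrants.** 708 − 123 = 585 entered through Step 1. The Step 2 size after the cut to 708 is not given, so every row below is an assumption. The 45% remission and 8% dropout rates are from the protocol's milestone table (K4), 40% remission is from H2, and the ratio 800/1500 is the original plan in SAP 3.3. The rows where half proceed have no source and serve as a stress case.

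| Assumption | From Step 1 | Step 2 total | Direct share |
|---|---|---|---|
| 585 × (1 − .45 − .08) | 275 | 398 | 31% |
| 585 × .92 × .55 | 296 | 419 | 29% |
| 585 × (1 − .40 − .08) | 304 | 427 | 29% |
| 585 × 800/1500 | 312 | 435 | 28% |
| 585 × .92 × .60 | 323 | 446 | 28% |
| Half of 275 proceed | 137 | 260 | 47% |
| Half of 296 proceed | 148 | 271 | 45% |
| Half of 304 proceed | 152 | 275 | 45% |

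**What pooling does to the estimate.** Pooled effect = (1 − w) × effect in Step 1-derived participants + w × effect in direct entrants, where w is the direct share. Suppose the effect is 2.0 points in the first group.

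- Effect 0 in direct entrants, w = .309: .691 × 2.0 = 1.38.
- Effect 4.0 in direct entrants, w = .309: 1.38 + .309 × 4.0 = 2.62.
- Effect 2.0 in both: pooling changes nothing.

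**Is the pooled test valid without a route term?** A simulation of 8,000 trials per setting used 296 + 123 participants, SD 8, no treatment effect, and route means 0, 2 or 4 points apart. Type I error was 0.048, 0.046 and 0.055, and bias was at most 0.004 points. Adding the route term reduced the standard error by at most 3% (0.815 to 0.792, at a 4-point route difference).

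**Precision of the restricted analysis.** Detectable difference at 80% power = 2.80 × 8 × √(2/n per arm).

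- Everyone, total 398 to 446: 2.25 to 2.12 points.
- Step 1-derived only, total 275 to 323: 2.70 to 2.49 points.
- Stress case, 271 against 148: 2.72 against 3.68 points.
- A route-by-treatment interaction would have to be about 4.8 to 4.9 points (5.5 in the stress case).

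**The case against.** A reader might infer that the Step 2 result is biased or does not answer its own question. The documents do not support that. SAP 3.1 itself places people who do not qualify for Step 1 in Step 2, SAP 3.3 and footnote 4 disclose them, and the hypotheses in SAP 2.2.2 compare augmentation with monotherapy without restricting Step 2 to failures of Step 1. Everyone is randomised within Step 2, so leaving route out does not bias the comparison. All of this stands.

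A reader might also worry about chance imbalance in route. If remission differed by 15 points between routes (an assumption), an imbalance at its 95% limit would move the remission difference by 1.96 × √(2 × .31 × .69/199) × 15 = 1.4 points, or 1.8 with 135 per arm and a 46% direct share. The 95% confidence half-width at 199 per arm and 40% remission is 1.96 × √(2 × .4 × .6/199) = 9.6 points, and it already reflects such imbalance. This is minor.

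Three further inferences go too far:

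- **Tolerability leavers entering Step 2 already in remission.** Protocol D2 1.j sets no score condition, but leavers complete the end-of-step assessments first, E1.b randomises those not remitted, and the inclusion criteria headed for both steps require current major depression and a PHQ-9 of at least 10. Numbers of leavers and relapsers are not given.
- **Direct entrants having fewer failed treatments.** They also needed two failed trials, and exclusion (e) covers earlier non-response to study drugs, so some may already have failed a Step 1 drug.
- **Route being ignored in the Step 2 randomisation.** SAP 3.2 lists site, referral source and age, but its blocks of 3 and 6 fit the three-arm Step 1. Step 2 strata are not separately described.

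What remains is the missing definition. The SAP gives two incompatible descriptions of the population and no analysis set, and the model text is ambiguous for 123 people.

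**Conclusion.** The point holds as one of definition and interpretation; it does not show bias. The Step 2 analysis set and baseline are undefined, and the ambiguity covers roughly 30% of Step 2: 28–31% if all those expected to move on do so, and 45–47% if only half do. Both ranges rest on an assumed Step 2 size. A literal reading would exclude randomised participants, against SAP 4.3 and the statement in SAP 3.2 that randomised participants are analysed.

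If everyone is analysed, the test is valid, but the estimate describes a mixture. It could differ noticeably from the effect in Step 1 non-remitters (1.4 or 2.6 against 2.0 points in the illustrations), and no planned output would reveal this. Whether the effect really differs by route cannot be judged from the documents, and the trial is too small to test it well. The SAP's flow figure was not available in the text reviewed.

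**What to change.** In SAP 6.2:

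1. Name all participants randomised in Step 2, direct entrants included, as the primary intention-to-treat Step 2 set. Define the Step 2 baseline as the last assessment before Step 2 randomisation. State the two-arm form of the remission model, which is now written only for three groups.
2. Add entry route (from Step 1 or direct) as a two-level baseline covariate in the Step 2 well-being and remission models, and in the fall and serious adverse event models where event counts allow. Two levels are enough; a finer split risks sparse cells.
3. Report the Step 2 contrasts in those who entered as Step 1 non-remitters as a pre-labelled sensitivity analysis, or as post hoc if analyses have already begun, without a formal interaction test. Say how early stoppers without a MADRS are classified; SAP 6.3 counts them as non-remitters.

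Reconcile SAP 3.1 and 5.3 with each other and with protocol V3.0, describing direct entry as a route that has since closed.

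The cost is SAP wording and some extra analysis. Route must be known already, since SAP 3.3 counts the direct entrants. The restricted analysis has a wider interval, as shown above. Keeping the full set primary means that it does not become a competing result.

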We will also examine **exploratory hypotheses**, such as whether there are baseline covariates which will help to significantly enhance the prediction of response to treatments, e.g., gender, race, treatment site (primary care vs. specialty clinic), social support, co-treatments. This will enhance the precision medicine implications of the study.

H2: serious adverse events, falls, and fall-related injuries are the safety outcomes. Cox models examining time to event (with Anderson & Gill⁶⁴ extensions for repeated events) will compare the treatment arms during both the acute phase and the continuation in terms of serious adverse events, falls, and fall-related injuries.

We will also compute rates of side effects in each arm, as specifically recommended by patient stakeholders. These data are not hypothesis-testing, but they support the patient-centered goal of allowing clinicians and patients to know what to expect in terms of side effects from treatment.

H3: Moderator analyses (Heterogeneity of Treatment Effects).

Confirmatory analysis (HT-1): Effectiveness and safety differences between treatment arms will be moderated by age. Specifically, with increasing age effectiveness differences between treatment arms will decrease, and safety differences between treatment arms will increase.

Rationale: Our stakeholders demand that we move past the current "one size fits all" paradigm of antidepressant prescribing. Precision treatment would greatly improve older adults' quality of life.

Data analysis plan for moderator testing: We will include the treatment by age group (<70 vs >70) by time interaction to the linear models described above to test for both the benefits and risks for the treatment alternatives.

We are well-powered for a confirmatory moderator analysis examining how age modulates the differences between treatment arms in comparative benefits and risks, because of our recruitment strategy aiming for equally-sized strata of ages (60-70 and >70). Age will be treated as a categorical variable, comparing relative benefits and risks of antidepressants in those aged <70 to those aged >70.

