2.2.2. Hypothesis

Theme 1: Benefits and risks of antidepressants: outcomes that matter for patients and clinicians

- 1. Effectiveness. Augmentation arms will show greater improvement than monotherapy arms for effectiveness outcomes.
 - a. Wellness outcome: Improved psychological well-being. (H1a)
 - b. Symptom outcome: Remission from depression (defined as MADRS ≤10 at Step end).
 (H1b)
- 2. Safety. Augmentation arms will have more tolerability and safety concerns (i.e., more serious adverse events) than monotherapy arms.
 - a. Serious adverse events (H2a), falls, and fall-related injuries (H2b) are the safety outcomes.

The primary analytic strategy is a test of specific treatment strategies (e.g., aripiprazole augmentation). More recently, a report on these strategies in mixed-age veterans with TRD (Mohamed et al, JAMA 2017) has suggested that augmentation approaches yield higher remission rates than does switch. The TRD field has, likewise, converged on the overarching question of whether augmentation is superior to switch, more so than the specific question of which augmentation approach is superior (e.g., Ruberto, Jha, & Murrough, "Pharmacological treatments for patients with treatment-resistant depression", Pharmaceuticals 2020; Voineskos, Daskalakis & Blumberger, "Management of treatment-resistant depression", Neuropsychiatr Dis Treat 2020) with a recent Cochrane systematic review (Davies et al, 2019) determining that augmentation strategies appeared efficacious while switch strategies had uncertain efficacy.

For this reason, a secondary analysis of each hypothesis will test the overall strategy of augmentation vs. switch. The two augmentation arms in Step 1 will be summed and compared to the switch arm.

Theme 2: Aging influences the balance of benefits and risks of antidepressant strategies.

3. Moderator analyses (Heterogeneity of Treatment Effect). Exploratory analysis (HT-1): Effectiveness and safety differences between treatment arms will be moderated by age. Specifically, with increasing age effectiveness differences between treatment arms will decrease, and safety differences between treatment arms will increase. In addition, the following potential moderators will be assessed: executive function, co-morbid medical burden, co-morbid anxiety, and degree of treatment resistance.

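### The one age-moderation term named in SAP 6.2 tests week-to-week drift for falls, not the stated hypothesis, and leaves serious adverse events with no defined test

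*SAP*

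**What the plan says.** - **Hypothesis (SAP 2.2.2, HT-1):** "with increasing age effectiveness differences between treatment arms will decrease, and safety differences between treatment arms will increase". This is a statement about treatment and age. It says nothing about a trend over weeks.
- **Test (SAP 6.2, hypothesis 3):** "treatment by age group (<70 vs >70) by time interaction to the linear models described above to test for both the benefits and risks". A further sentence adds a model with continuous age but names no interaction. Protocol section H1, under its H3 heading, has the same wording: "We will include the treatment by age group (<70 vs >70) by time interaction to the linear models described above".
- **H1a, well-being (SAP 6.2):** the factors are age, "time (baseline, end of Active phase of Step 1) by treatment group (3 levels").
- **H1b, remission (SAP 6.2):** "2*3 (age by treatment group) generalized linear models with a logit link function". There is no time factor.
- **H2a, serious adverse events (SAP 6.2):** a Cox model extended to repeated events. Neither age nor an age interaction is named.
- **H2b, falls (SAP 6.2):** "The factors will be treatment group and time (week 2, 4, 6, 8 or 10"). Age group and clinic strata are "included in the model as well as the fall history obtained at baseline". Injuries use the same model with a simple logistic link, run during each two-week period.
- **Harms in the protocol (section H1, hypothesis H2):** Cox models for serious adverse events, falls and injuries alike.
- **Status:** SAP 2.2.2 and 6.2 call the age analysis exploratory. The protocol's H3 text calls it confirmatory and well powered.

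**The concern.** The same interaction answers different questions in different models, because time does not mean the same thing in each. With time as baseline versus step end, the three-way term is age moderation of the treatment effect on change, which is what HT-1 claims. With five follow-up fortnights and baseline only a covariate, moderation of fall risk is carried by treatment by age. The three-way term then measures only how that moderation varies between fortnights. Where the model has no time factor, the term cannot be formed.

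Aim 2 concerns how age changes the balance of benefit and risk. As written, the named test for falls is not a test of HT-1, and serious adverse events have none. A non-significant three-way result could be misread as evidence that age does not alter fall risk between arms, and testing any other term would be an unplanned choice.

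**Working it through.** **1. The plan's own figure.** The documents give no power for age moderation of harm. The protocol's only moderator figure (power above 85%) is for well-being and remission. It cannot be reproduced uniquely, because neither alpha nor the exact contrast is stated. For 2.3 points, with SD of change √(8² + 8² − 2·0.5·8·8) = 8, 250 per arm-by-age cell and alpha .05:

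- As a difference of differences, SE = 8√(4/250) = 1.01 and power is 62%.
- As the simple effect at age 60–70, SE = 8√(2/250) = 0.72 and power is 90%.
- As an excess over main effects (contrast 4.6), power is over 99%.

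None of these bears on falls or serious adverse events.

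**2. What the named term tests in the falls model.** For a fall in fortnight t, with treatment T and age group A:

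logit P = β₀ + β₁T + β₂A + β₃TA + τₜ + (T by time) + (A by time) + γₜTA

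The named test is of all γₜ = 0. Moderation that is steady on the logit scale means β₃ ≠ 0 with all γₜ = 0. The null of the named test is then true, so it should reject at its nominal level whatever the size of β₃.

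**3. Simulation of one pairwise arm comparison.**

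Inputs from the documents:

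- Fall rate 20% (protocol power table).
- Original size 1500/6 = 250 per arm-by-age cell.
- Revised size (708 − 123)/6 = 585/6 = 97.5 per cell if evenly split (SAP 3.3), run at 97.

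Assumptions not in the documents:

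- The 20% is a 10-week risk, which gives 4.8% per fortnight. The protocol states no time window.
- Person random effect SD 1.
- Fall yes/no in place of the cumulative logit, with no fall-history or clinic covariates.
- Harm only in one arm over age 70, with the same odds ratio in every fortnight.

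The fit was a logistic model with person-clustered robust Wald tests, alpha .05, 1000 runs. Treatment by age was taken from the model that also held the three-way linear-time term, with time centred so that it averages over weeks.

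| Per cell | Odds ratio | 10-week risk, harmed cell | Three-way, linear time | Three-way, 4 df | Treatment by age |
|---|---|---|---|---|---|
| 250 | 1 | 20% | 5.2% | 5.0% | 4.3% |
| 250 | 2 | 33% | 5.1% | 4.7% | 62% |
| 250 | 3 | 42% | 5.7% | 5.3% | 96% |
| 97 | 1 | 20% | 5.3% | 3.2% | 6.2% |
| 97 | 2 | 33% | 4.9% | 3.4% | 30% |
| 97 | 3 | 42% | 4.8% | 3.0% | 65% |

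At 97 per cell, 8–12% of the 4-df fits were unusable because of sparse cells and were left out.

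**4. The other outcomes, by comparison of the text.**

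| Outcome | Time factor | Three-way term possible? | Treatment by age present? |
|---|---|---|---|
| H1a well-being | baseline, step end | yes, and correct | not needed |
| H1b remission | none | no | yes, in the 2*3 model, but not named for H3 |
| H2a serious adverse events | none | no | no; no age term named |
| H2b falls, SAP 6.2 | weeks 2–10 | yes, but tests drift | not named as the test |
| H2b injuries, SAP 6.2 | depends on reading | only if fitted as repeated measures | not named as the test |
| All harms, protocol | none (Cox) | no | not named |

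Reading the linear models in the H3 sentence as the H1a ANOVA alone does not help. The sentence promises a test of risks, and no risk outcome would then be covered.

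**The case against.** - **A falls model with the three-way term would normally also contain treatment by age.** This stands. In the simulation that lower-order term found the effect. A reader might infer that a steady moderation must go unseen or be reported as absent. The documents do not support that: the protocol promises a comparison of benefits and risks below and above 70, and a report of all prespecified moderator analyses. What is missing is the naming of the term as the H3 test. Its meaning also depends on coding, since with a reference week it describes that fortnight only.
- **Remission.** A reader might infer that H3 has no test there. The model is already age by treatment, and the protocol's remission scenario (13 points at 60–70, none above 70) is a two-way contrast. Only the name is missing. Remission is also a benefit, so it says nothing about harm.
- **The protocol.** The drift argument does not carry over, because its harm models are Cox models without a week factor. There the term cannot be formed at all, which is a different gap.
- **Which falls model applies.** SAP 6.1.1 says falls information was not collected in the acute phase and turns to a logistic model with no week factor named. SAP 6.2 models weeks 2 to 10. The drift finding holds for the SAP 6.2 model.
- **The low power of the three-way test follows from simulating a steady effect.** True, but HT-1 states no time trend. The treatment-by-age figures do depend on the assumed odds ratios and are modest at the revised size.

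**Conclusion.** The point holds for falls as modelled in SAP 6.2, and for injuries if they are fitted as repeated measures. There the named term tests something other than HT-1, and its power against a steady moderation is about 3–6%, in effect its type I error. That result follows from the model and does not hinge on the assumed rates. The contrast with treatment by age (30–65% at the revised size, 62–96% at the original) rests on assumed odds ratios of 2 to 3 confined to age over 70 and on the assumptions listed with the simulation. Age moderation of serious adverse events has no defined test in the SAP. In the protocol the named term cannot be formed for any harm. Remission needs only to have its existing term named.

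Severity is moderate. The primary treatment comparisons are unaffected and the SAP labels H3 exploratory, but the protocol's confirmatory label makes an undefined or mismatched test harder to leave as it is.

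**What to change.** Replace the H3 sentence in SAP 6.2 with one term per outcome:

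- **H1a:** treatment by age by time.
- **H1b:** treatment by age in the logit model.
- **H2a:** age and treatment by age in the Cox model.
- **H2b, falls and injuries:** treatment by age averaged over weeks, with time as a main effect. Keep the three-way term, if at all, as a secondary check of drift.

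Use the same terms for continuous age and for the other moderators in SAP 2.2.2. In the protocol's H3 text, name treatment by age for remission and for the Cox harm models. Say whether injuries are fitted as one repeated-measures model or fortnight by fortnight. Reconcile SAP 6.1.1 with SAP 6.2 on whether acute-phase falls data exist, and give H3 one status in both documents.

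The cost is wording only, with no new data and no change to sample size or primary tests. A footnote to SAP 4.3 describes analyses already run, so the change should be dated and should state whether any H3 results had been seen.
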